4.1 Diagnostic criteria of Western Medicine

4.1.1 Diagnostic criteria for coronary heart disease

Referring to the Guidelines for the Diagnosis and Treatment of Chronic Stable Angina issued by the Chinese Medical Association in 2007, the Diagnosis of Stable Ischemic Heart Disease by 2012 ACP/ACCF/AHA/AATS/PCNA/STS: Clinical Practice Guidelines, and the Guidelines for the Management of Stable Coronary Artery Diseases issued by 2013 ESC, we can diagnose coronary heart disease by conforming to any of the following:

- (1) There is a clear history of old myocardial infarction, PCI or bypass.
- (2) Coronary angiography (results indicate that at least one coronary artery is stenosed and the lumen is stenosed more than 50%) or coronary CTA indicates that the lumen is stenosed more than 50%.

4.1.2 Diagnostic criteria for angina pectoris

Referring to the Guidelines for the Diagnosis and Treatment of Chronic Stable Angina Pectoris issued by the Editorial Board of the Chinese Journal of Cardiovascular Diseases in 2007, the Society of Cardiovascular Diseases of the Chinese Medical Association:

When physical activity or mental stress occurs, coronary artery blood flow can not meet the needs of myocardial metabolism, leading to angina attack induced by myocardial ischemia. Resting or taking nitroglycerin can alleviate it. Chronic stable angina pectoris refers to the degree, frequency, nature and inducing factors of angina

pectoris attacks in 1 to 3 months without significant changes in subjects.

Referring to the International Heart Association and WHO Joint Thematic Group on Standardization of Clinical Nomenclature, "Criteria for Nomenclature and Diagnosis of Ischemic Heart Disease" [2].

Tired angina pectoris: Tired angina pectoris is characterized by a brief onset of chest pain induced by exercise or other conditions that increase myocardial oxygen demand. After rest or sublingual administration of nitroglycerin, the pain often disappears rapidly. There are three types of fatigue angina pectoris:

First-onset fatigue angina pectoris: the course of the disease is less than one month.

Stable fatigue angina pectoris: the course of the disease is stable for more than one month.

Deteriorating fatigue angina pectoris: The number, severity and duration of fatigue induced by the same degree of fatigue suddenly increased.

Spontaneous angina pectoris: The characteristic of spontaneous angina pectoris is that there is no significant relationship between chest pain attack and the increase of myocardial oxygen demand. Compared with fatigue angina pectoris, the pain generally lasts longer and is more severe, and is not alleviated by nitroglycerin. There was no change of enzymes in this type. There were some temporary S-T segment depression or T wave changes in ECG. Spontaneous angina pectoris can occur alone or in combination with fatigue angina pectoris.

The frequency, duration and degree of pain in subjects with spontaneous angina pectoris may have different clinical manifestations. Sometimes the subjects may have sustained chest pain attacks, similar to myocardial infarction, but without characteristic changes of electrocardiogram and enzymes. Temporary S-T elevation occurs in some subjects with spontaneous angina pectoris, often referred to as variant angina pectoris. However, this name cannot be used when the ECG pattern is recorded in the early stage of myocardial infarction.

Initial fatigue angina pectoris, worsening fatigue angina pectoris and spontaneous angina pectoris are collectively referred to as "unstable angina pectoris".

4.1.3 Classification criteria for angina pectoris

Reference to Canadian Cardiovascular Society (CCS) Angina Severity Classification [4] Standard。

I : General physical activity does not cause angina pectoris, such as walking and going upstairs, but tension, rapid or sustained exertion can cause the onset of angina pectoris.

II: Daily physical activity is slightly restricted. Walking fast or upstairs, climbing high, walking after meals or upstairs, walking in cold or wind, and emotional excitement can cause angina or only occur within a few hours after waking up. It is limited to walk more than 200 meters or climb stairs above one floor at normal speed.

III: Daily physical activity is obviously limited, and angina pectoris can occur when walking 100-200 m at normal speed or climbing a staircase.

IV: Angina symptoms can occur when you are slightly active or at rest.

This table is cited from the guidelines for the management of chronic stable angina pectoris (ACC/AHA/ACP-ASIM, American College of Cardiology/American Heart Association/American College of Internal Medicine and American Medical Association).

4.2. Differentiation Standard of Traditional Chinese Medicine

According to the prescription composition and function of Xinnaoning Capsule, and referring to the Guiding Principles for Clinical Research of Coronary Heart Disease and Angina Pectoris Treated with Chinese Medicine and Natural Medicine in 2011, the syndrome differentiation and diagnosis criteria of Angina Pectoris with Qi stagnation and blood stasis syndrome were drawn up:

Diagnostic criteria of chest arthralgia in traditional Chinese medicine

①Chest pain, even chest pain thoroughly back chest pain, even chest pain thoroughly back;

②The lighter ones only feel chest tightness, suffocation and breathlessness.;

Qi stagnation and blood stasis syndrome:

Main symptoms: chest pain, chest tightness

Secondary symptoms: chest swelling, palpitation, shortness of breath, purple lips, fatigue, dizziness, dark purple veins at the bottom of the tongue, irritability.

Tongue image: dark tongue. Pulse: astringent.

One of the main symptoms, two of the secondary symptoms and supporters of tongue and vein can be diagnosed.

4. 3. Angina Pectoris Integral Scoring Method

(Angina Pectoris)		
	0	0
	weekly	2
1. Frequency:	1-3times per day or CCS II	4
	≥4times per day or CCSIII	6
	0	0
	Every pain lasting ≤5min。	1
2. Duration:	Every pain lasting >5, and <10min。	2
	Every pain lasting ≥10min	
	nothing	0
	The pain is not serious and does not affect daily life.	1
3. Degree of pain:	The pain is severe and needs nitroglycerin.	2
	Severe seizures affect daily activities (such as dressing, defecation, etc.).	3
	nothing	0
4.Nitrogl	1-4tablets per week	1
ycerin	5-9tablets per week。	2
dosage	≥10tablets per week	3

4. 4. TCM Syndrome Integral Scoring Method

Main symptom	Chest pain	
0: nothing
 
2: The seizure is relieved by rest and does not affect daily life.
 
4: Medication should be taken during seizures and normal activities can continue after remission.
 
6: Frequent seizures affect daily activities (such as clothing, eating, walking, fecal symptoms)

	Chest tightness	
0: nothing
 
2: Occasionally chest tightness can be alleviated by oneself
 
4: Chest tightness attacks are frequent, but do not affect life and work
 
6: Chest tightness continues to puzzle, affecting life and work

Secondary symptom	palpitation	0: nothing 1: Occasional palpitation can be alleviated by itself 2: Frequent episodes, but able to work persistently 3: Palpitations persist, affecting life and work
	pant	0: nothing 1: Short breath after general activities 2: Short breath after a little exercise 3: Normally inactive and short of breath
	Chest and side fullness	0: nothing 1: Occasional distension and discomfort, short time, self-relief 2: Depressed for a long time, occasionally need to take medicine. 3: Recurrent seizures can only be alleviated by taking medicine.
	Mental exhaustion and fatigue	0: nothing 1: Mentally depressed, weak in strength teaching, can adhere to daily work and activities. 2: Mental weakness, physical weakness, reluctant to stick to work 3: Mental energy is so weak that it is difficult to stick to daily work.
	Purple lips	0: no 1: yes
	dizziness	0: no 1: yes
	Sublingual venation	0: Lavender 1: Dark purple with bruises
	Impatient and irritable	0: no 1: yes
	Tongue manifestation	Dark others _____
	Pulse condition	uneven/ string-like pulse others _____

Note: Tongue and pulse are only described and not scored.

4.5 Seattle Angina Questionnaire,SAQ。

4.6 Participant selection criteria

1) Referring to the Guidelines for the Diagnosis and Treatment of Chronic Stable Angina [6], issued by the Chinese Medical Association in 2007, the diagnosis of stable ischemic heart disease in 2012 ACP/ACCF/AHA/AATS/PCNA/STS: Guidelines for Clinical Practice, and Guidelines for the Management of Stable Coronary Artery Disease in 2013 ESC, the diagnosis of coronary heart disease can be made in accordance with any of the following:

(1) Has a clear history of old myocardial infarction, or PCI history, or bypass history;

(2) Coronary angiography (results indicate that at least one coronary artery is stenosed and the lumen is stenosed more than 50%) or coronary CTA suggests that the lumen is stenosed more than 50%.

2) Those who met the diagnostic criteria of chronic stable angina pectoris: those who had a history of angina pectoris more than 1 month and had no significant changes in the degree, frequency, nature and inducing factors of angina pectoris;

3) The severity of angina pectoris of the Canadian Cardiovascular Society (CCS) was classified as Grade I-III, and the number of episodes per week was more than two.

4) The syndrome differentiation of TCM is Qi stagnation and blood stasis syndrome.

5) Age between 30 and 79 years old;

6) Sign the informed consent.

4.7 Subject exclusion criteria

1) Severe cardiopulmonary insufficiency (grade III, IV, severe abnormal pulmonary function);

2) Poor control of hypertension (systolic blood pressure (> 160 mmHg) or diastolic blood pressure (> 100 mmHg) after treatment;

3) Severe primary diseases such as ALT, AST (> 1.5 times the upper limit of normal value) or Cr (> upper limit of normal value), hematopoietic system and so on.

4) Acute myocardial infarction within 3 months after interventional therapy;

5) Other factors affecting ST-T changes in ECG, such as myocardial hypertrophy, left bundle branch block, etc.

6) Cardiac pacemaker;

- 7) Chest pain caused by other causes (moderate anemia, hyperthyroidism, etc.);
- 8) Pregnancy, lactation or pregnancy planning;
- 9) allergic constitution or allergic to known ingredients of research drugs;
- 10) Those who participated in other clinical drug trials within one month;
- 11) Researchers consider it inappropriate to participate in clinical research.

4.8 Exfoliation excluded cases

4.8.1 The withdrawal of the researcher's decision

Subject withdrawal from the study refers to the decision to withdraw the case from the study according to the judgement of the researcher when the selected subjects are unsuitable for further study in the course of the study.

① In the study, patients with aggravated or aggravated conditions, such as increased number of angina attacks, prolonged duration of each attack or aggravated pain, must take emergency treatment measures such as adjusting treatment drugs, hospitalization or surgery;

② In the study, some complications, complications or special physiological changes occurred in the subjects, and it was not appropriate to continue the study;

③ Prohibited drugs prescribed by the scheme were used in the study。

④ In the study, if angina symptoms worsened in the subjects, those who were judged by the researchers to need to take other angina medicines or increase the dosage of drugs were withdrawn as invalid cases。

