4.8.2 Subjects withdraw spontaneously

According to the informed consent, the subjects have the right to withdraw from the study halfway, or they have not explicitly proposed to withdraw from the study, but no longer accept medication and testing and lost interviews, which also belongs to "withdrawal" (or "fall off"). The reasons for their withdrawal should be understood and recorded as far as possible. Such as: poor self-efficacy; intolerable to some adverse reactions; unable to continue to accept clinical research; economic factors; or missing interviews without explaining the reasons.

Whatever the reason, the case records should be kept for the withdrawal cases, and the final test results should be transferred to the final results. The efficacy and adverse reactions of the withdrawal cases should be analyzed by a full data set. All withdrawal cases should be filled in the case report form, the conclusion form and the reasons for withdrawal. In general, there are six kinds, namely, adverse events

(including adverse drug reactions and allergic reactions), lack of efficacy (deterioration or complications), violation of research programs, loss of interviews (including withdrawal of the subjects themselves), suspension of the applicant and others.

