5.9 Regulations on combined use of drugs

1. In addition to experimental medication, nitroglycerin tablets can be used to alleviate symptoms when angina attacks. For drugs already used to treat coronary heart disease before inclusion, such as antiplatelet drugs, angiotensin-converting enzyme inhibitors (ACEI) or angiotensin II receptor antagonists (ARB), statins, calcium antagonists, beta-blockers and long-acting nitrates, the original varieties and dosages can be continued without adjustment. During the study period, it is forbidden to add any other Chinese and Western medicines which have therapeutic effects on angina pectoris of coronary heart disease.

2. For the original and emerging diseases requiring drug treatment, the drug combination should be recorded in the medical record and CRF in detail, including the generic name of the drug, dosage and method of administration, the starting time of drug use and the reasons for its use.

6. Observation items

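### Use of a forbidden angina drug has no outcome of its own, so the carry-forward rules can bring a score taken on that drug into the primary analysis

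*Protocol*

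**What the plan says.** **Protocol 4.8.1 (withdrawal by the researcher).** Item 3 is a bare trigger, "Prohibited drugs prescribed by the scheme were used in the study", with no outcome. Item 4 covers subjects whose angina worsened and who were "judged by the researchers to need to take other angina medicines or increase the dosage of drugs were withdrawn as invalid cases". Invalid is a category of the primary scale in 8.1.1, so item 4 fixes the primary outcome as failure.

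**Protocol 5.9.** During the study "it is forbidden to add any other Chinese and Western medicines which have therapeutic effects on angina pectoris of coronary heart disease". No other class of drug is forbidden there.

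**Protocol 4.8.2.** "Whatever the reason, the case records should be kept for the withdrawal cases, and the final test results should be transferred to the final results". Withdrawn subjects also stay in the full data set, for efficacy as well as for adverse reactions. It stands under the heading on spontaneous withdrawal, but its list of withdrawal reasons includes lack of efficacy, protocol violation and suspension by the applicant.

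**Protocol 10.2.1(3) and 10.2.3(2).** Missing primary data are filled from the previous measurement, and the FAS is the main efficacy set.

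**Protocol 6.4.3 and 6.4.4.** At weeks 4, 8 and 12 the same visit records concomitant medication and symptoms and rates the curative effect.

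**The concern.** A subject who starts another angina medicine can reach the primary analysis by two routes. If worsening is recorded and the investigator judges the drug necessary, item 4 makes the subject a failure. If the subject is simply found to have taken it, for instance self-started or prescribed elsewhere, item 3 applies, no outcome is given and the general carry-forward rules take over. A subject may meet both items, and nothing says which governs.

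Visits are four weeks apart, so use may come to light at a visit where the symptom score is also taken. Nothing restricts the carried-forward score to one obtained before the added drug. A score improved by that drug can then be credited to the randomised arm. If subjects with little relief are those who add drugs, and there are more of them on placebo, the placebo response rises and the difference narrows.

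**Working it through.** **1. Tracing the rules to the primary endpoint**

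| Situation | Rule | Stated outcome | Result in FAS |
|---|---|---|---|
| Worsened, judged to need another angina drug | 4.8.1 item 4 | Invalid | Failure |
| Took a forbidden angina drug, no worsening recorded | 4.8.1 item 3 | None | Last score carried forward (4.8.2, 10.2.1(3)) |
| Both apply | Items 3 and 4 | No precedence | Depends on classification |

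Read literally, the opening of 4.8.2 ("Whatever the reason, the case records should be kept for the withdrawal cases", continuing "the final test results should be transferred to the final results") even competes with item 4.

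Other sections do not close the gap:
- 4.8.3 does not list forbidden-drug use among its exclusion criteria.
- 7.1.2 makes a subject non-curative only for quitting through aggravation after more than 4 weeks, and only in the PPS.
- 10.1 takes absence of major violations into account for the PPS, which leaves the FAS unchanged.
- 5.6(8) checks combined drug use before blind review but states no scoring rule.

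**2. Reproducing the planned sample size (3.2)**

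Inputs: 67.5% and 84.3%, alpha 0.05 two-sided, 80% power (the printed 1-β=0.2 reproduces only as β=0.2).

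n = [67.5×32.5 + 84.3×15.7] / 16.8² × f = 3517.26 / 282.24 × f = 12.462 × f

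f = 7.85 gives 97.8 and f = 7.9 gives 98.4, the protocol's figure. The plan then enrols 120 per arm.

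**3. Base power at 120 per arm (normal approximation, unpooled variance)**

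SE = √[(0.675×0.325 + 0.843×0.157)/120] = 0.0541

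z = 0.168/0.0541 = 3.10; power = Φ(3.10 − 1.96) = 87%. At 98.4 per arm it is 80%.

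**4. Illustration of size (all rates of use are assumptions)**

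Take 67.5% and 84.3% as the rates when these subjects count as failures. Let c and t be the proportions of control and test subjects on the item 3 route, and q the share of them carried forward as effective:

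control = 0.675 + c·q; test = 0.843 + t·q; difference = 0.168 − (c − t)·q

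| c / t | q | Control | Test | Difference (points) | Power |
|---|---|---|---|---|---|
| 2% / 1% | 0.5 | 68.5% | 84.8% | 16.3 | 86% |
| 2% / 1% | 0.9 | 69.3% | 85.2% | 15.9 | 85% |
| 5% / 2% | 0.5 | 70.0% | 85.3% | 15.3 | 82% |
| 5% / 2% | 0.9 | 72.0% | 86.1% | 14.1 | 78% |
| 8% / 3% | 0.5 | 71.5% | 85.8% | 14.3 | 78% |
| 8% / 3% | 0.9 | 74.7% | 87.0% | 12.3 | 69% |
| 10% / 5% | 0.5 | 72.5% | 86.8% | 14.3 | 80% |
| 10% / 5% | 0.9 | 76.5% | 88.8% | 12.3 | 72% |

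With c = t the term (c − t)·q is zero and the difference stays at 16.8 points.

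**5. A different base**

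Apply the planned rates only to subjects who add no drug, with 5% (test) and 10% (control) adding one. Power here uses a pooled-variance formula.
- All failures: test 0.95×84.3 = 80.1%, control 0.90×67.5 = 60.8%, difference 19.3 points, power 91%.
- All carried forward as responders: test 80.1 + 5 = 85.1%, control 60.8 + 10 = 70.8%, difference 14.3 points, power 77%.
- Equal use of 5% per arm: difference 16.0 points under either scoring; power 79% if failures, 84% if carried forward.

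**The case against.** A reader might infer that items 3 and 4 score the same act in contradictory ways. They do not. Item 4 requires worsened angina and a researcher's judgement of need, and the drug need not have been taken. Item 3 is a protocol violation with no worsening required, and 4.8.2 lists deterioration and violation as separate reasons. A reader might also infer that item 3 itself orders carry-forward; it is silent, and the rule comes from 4.8.2 and 10.2.1(3). The latter opens by leaving the filling method to statistical and professional judgement. Nor is a false responder certain, since the last score may precede the added drug.

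There are further points against the concern. Blind review already checks combined drugs (5.6(8)), 10.2.3(7) compares forbidden-drug use between arms, 10.2.3(11) allows covariate adjustment and lists combined medication, and a PPS analysis is planned. Keeping scores after a violation can be defended as close to intention-to-treat. If use is commoner on placebo, the effect is conservative and the fix would favour the test drug. Detail could also sit in an analysis plan that is not shown.

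Most of this stands as a limit on the claim. It does not remove the gap. The protocol states a carry-forward rule and a failure rule for the same drugs, sets no precedence, and does not bar a score taken on the added drug. That is a defect in what is written, not detail deferred. None of the listed checks sets the FAS outcome.

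**Conclusion.** The point holds in limited form. The protocol treats a worsened subject's need for another angina medicine as failure, yet lets actual use of a forbidden one fall to carry-forward. Classification by the investigator can decide the primary outcome, and a score improved by the added drug can count as response.

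It would be tempting to conclude that the trial loses a known amount of power or is biased against the test drug. The documents do not support that. They give no rate of use, no split between arms, and no indication whether the planned 67.5% and 84.3% already count such subjects as failures. Under assumed heavier use on placebo, the loss runs from about half a point (2% v 1%, q = 0.5) to 4.5 points (8% v 3% or 10% v 5%, q = 0.9). In the 5% v 2% case power is 82-78%, close to the planned 80%. With equal use the difference does not shrink. The matter should be corrected because the rule is ambiguous on the primary endpoint and cheap to settle, not because a large loss has been shown.

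**What to change.** Reconcile 4.8.1 items 3 and 4 with 4.8.2 and 10.2.1(3) through one outcome rule for the FAS primary analysis:

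- No score taken after the first dose of an added angina medicine forbidden by 5.9 is carried forward.
- Such a subject is scored invalid at week 12, as in item 4, whoever started the drug.
- This rule takes precedence over carry-forward.
- It is applied at blind review from the recorded start dates of concomitant drugs.
- A sensitivity analysis carries forward the last score before the added drug.

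This changes outcome scoring only, not who is withdrawn or what treatment anyone receives. The cost is wording in the protocol or analysis plan, plus one extra analysis. Start times of combined drugs are already to be recorded (5.9) and combined drug use is already checked before database lock (5.6(8)). The downside is that a subject who took such a drug for a reason other than angina also counts as a failure, in either arm; the sensitivity analysis shows how much that matters.

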4.8.2 Subjects withdraw spontaneously

According to the informed consent, the subjects have the right to withdraw from the study halfway, or they have not explicitly proposed to withdraw from the study, but no longer accept medication and testing and lost interviews, which also belongs to "withdrawal" (or "fall off"). The reasons for their withdrawal should be understood and recorded as far as possible. Such as: poor self-efficacy; intolerable to some adverse reactions; unable to continue to accept clinical research; economic factors; or missing interviews without explaining the reasons.

Whatever the reason, the case records should be kept for the withdrawal cases, and the final test results should be transferred to the final results. The efficacy and adverse reactions of the withdrawal cases should be analyzed by a full data set. All withdrawal cases should be filled in the case report form, the conclusion form and the reasons for withdrawal. In general, there are six kinds, namely, adverse events

(including adverse drug reactions and allergic reactions), lack of efficacy (deterioration or complications), violation of research programs, loss of interviews (including withdrawal of the subjects themselves), suspension of the applicant and others.

